1.1 Protocol Amendment: Summary of Changes

The purpose of this amendment is to:

- Section 3.1 Safety Information: Add new subsection for safety monitoring requirements.

Rationale: To comply with an FDA requested, TNF-inhibitor class wide exploration of the rare appearance of malignancy in patients ≤ 30 years of age.

- Section 6.4.5 Prior and Concomitant Medications: Add new data collection requirements for events of malignancy in patients ≤ 30 years of age.

Rationale: To comply with an FDA requested TNF-inhibitor class wide exploration of the rare appearance of malignancy in patients ≤ 30 years of age.

- Section 7.1.1 Adverse Events: Clarify that elective surgery/procedures performed during the registry period will not be considered SAEs if the surgery/procedure is performed for a pre-existing condition and the surgery/procedure was planned prior to enrollment in the registry.

Rationale: To align with current AbbVie safety standards.

- Section 7.4 Adverse Event Collection Period: Clarify the duration of follow-up for patients who develop an adverse event of interest or SAE.

Rationale: Follow-up duration is based on post-marketing reporting requirements.

- Section 7.5 Adverse Event Reporting: Add new reporting requirements for serious and nonserious events of malignancy in patients ≤ 30 years of age.

Rationale: To comply with an FDA requested, TNF-inhibitor class wide exploration of the rare appearance of malignancy in patients ≤ 30 years of age.

- Section 7.6 Pregnancy: The data collection period for pregnancy was updated to be from the date of first dose through 150 days following the last registry dose. The requirement to register for the AbbVie sponsored pregnancy registry for US, Puerto Rico and Canada was removed. In addition, the time period to report any event of pregnancy, spontaneous abortion, stillbirth, or congenital anomaly was updated to be within 24 hours.

Rationale: Admission to the pregnancy registry is no longer available and the reporting time for pregnancy and pregnancy related events was updated to reflect current standard SAE reporting requirements.

- Correct minor typographical and grammatical errors throughout the document.
- Administrative Changes:
 - Incorporate Administrative Change 6:
 - Title page: Update contact information and remove GCP requirement.
 - Section 6.0: Describe when an Investigator may become a Health Care Provider (HCP) in the Investigational Plan.
 - Section 6.4.5 Concomitant Medications: Add criteria regarding interventional clinical trials.
 - Section 6.5 Withdrawal of Patients from Registry: Explain how to complete the eCRF pages for discontinued or lost to follow-up patients.
 - Section 7.0 Adverse Events/Adverse Event Reporting: update the reporting period for serious adverse events and adverse events of interest to be consistent within the protocol.
 - Section 7.7 Data Collection Procedures for Patients Who Re-enroll in the Registry: Clarify event reporting procedures for patients who re-enroll into the registry.
 - Section 12.0 Completion of Registry: Clarify the definition of registry completion.

- Incorporate Administrative Change 7:
 - Change Sponsor from Abbott Laboratories (Abbott) to AbbVie in all instances found within the protocol except where outside documents are referenced and include new Sponsor address.

For an itemized list of all changes made to the protocol under this amendment, please refer to [Appendix G](#).

3.0 Introduction

Crohn's disease (CD) encompasses a spectrum of clinical and pathological processes manifested by focal asymmetric, transmural, and occasionally, granulomatous inflammation affecting any segment of the gastrointestinal tract.¹ The prevalence of CD is approximately 140/100,000 in the United States (US) and 40 – 140/100,000 in the European Union (EU).² The incidence is lower in developing countries. The disease can affect persons of any age and onset is most common in the second and third decades. Males and females are affected equally. The risk for disease is higher in some ethnic groups.³ CD is neither medically nor surgically curable thus requiring therapeutic approaches to maintain symptomatic control, improve quality of life, and minimize short and long-term toxicity and complications.⁴ Despite the relatively low incidence, the cost of therapy for these subjects is estimated at two billion dollars annually in the US.⁵

No single etiologic agent has been identified as the cause for disease. There is evidence of a genetic predisposition as well as a strong association with smoking.⁶ Current theories propose environmental factors in genetically predisposed hosts. The mechanism is thought to be a predisposition to an unregulated immune response to protein antigens that are present in normal intestinal microbial flora of the food stream. This can arise from a number of different immunologic defects that all result in a disease marked by excessive Type 1 T helper (Th1) T-cell response (with increased production of tumor necrosis factor-alpha [TNF- α], interleukin-2 [IL-2], and interleukin-12 [IL-12]).⁷

TNF is a naturally occurring cytokine that is involved in normal inflammatory and immune responses. Elevated levels of TNF play an important role in pathologic inflammation. There is considerable evidence for the efficacy of anti-TNF agents in CD, which includes infliximab (Remicade) use for the treatment of CD.^{8,9}

Adalimumab is a recombinant human immunoglobulin (IgG1) monoclonal antibody containing only human peptide sequences. Adalimumab is produced by recombinant DNA technology in a mammalian cell expression system. It consists of 1330 amino acids and has a molecular weight of approximately 148 kilodaltons.

Adalimumab binds specifically to TNF and neutralizes the biological function of TNF by blocking its interaction with the p55 and p75 cell surface TNF receptors. Adalimumab is comprised of fully human heavy and light chain variable regions, which confer specificity to human TNF, and human IgG1 heavy chain and kappa light chain sequences.

Adalimumab binds with high affinity and specificity to soluble TNF- α but not lymphotoxin (TNF- β).

Adalimumab also modulates biological responses that are induced or regulated by TNF. After treatment with adalimumab, levels of acute phase reactants of inflammation (C-reactive protein [CRP] and erythrocyte sedimentation rate [ESR]) and serum cytokines rapidly decrease. Subjects treated with adalimumab usually experience improvement in these laboratory indicators of chronic inflammation.

As of 06 Nov 2009, adalimumab has been evaluated in approximately 24,228 subjects with rheumatoid arthritis (RA), psoriatic arthritis (PsA), ankylosing spondylitis (AS), psoriasis (Ps) and CD, juvenile rheumatoid (idiopathic) arthritis (JRA/JIA), hidradenitis suppurativa (HS), and ulcerative colitis (UC). Adalimumab is approved for the treatment of RA, AS, PsA, CD, Ps and JIA in the EU and US.¹⁰

Humira[®] (adalimumab) was approved for the treatment of CD by the US Food and Drug Administration on 27 Feb 2007 and received the European marketing authorization approval on 04 Jun 2007. Approval was based on four controlled clinical studies that showed that adalimumab was well tolerated and the pattern and frequency of adverse events (AEs) were comparable to those seen in the other populations previously studied. Refer to the most current local product label for a summary of these studies and a comprehensive explanation of the AE profile.¹¹

Fatalities, serious infections, and sepsis have been reported with the use of TNF antagonists. Many of the serious infections have occurred in subjects on concomitant immunosuppressive therapy that, in addition to their underlying immune disorder, could predispose them to infections. Tuberculosis (TB) has also been observed in subjects

treated with TNF antagonists, including adalimumab. The event rate for TB in the CD development program is consistent with the global adalimumab rate.¹¹

TNF antagonists, including adalimumab, have been associated with cases of demyelinating disease. Serious allergic adverse reactions have been reported in subjects following subcutaneous administration of adalimumab.¹⁰

In the controlled portions of clinical trials of TNF-antagonists, more cases of malignancies including lymphoma and non-melanoma skin cancer have been observed among patients receiving a TNF-antagonist compared with control patients. However, the occurrence was rare.¹² Furthermore, there is an increased background lymphoma risk in rheumatoid arthritis patients with long-standing, highly active, inflammatory disease, which complicates the risk estimation.¹³⁻¹⁵ Post-marketing cases of rare malignancies usually associated with immunosuppression and malignancies that are not usually observed in children and adolescents have been reported with use of TNF antagonists including adalimumab. These case reports are derived from a variety of sources including registries and spontaneous post-marketing reports.¹⁰ Rare post-marketing cases of hepatosplenic T-cell lymphoma have been identified in patients treated with TNF-antagonists including adalimumab.^{18,19} This rare type of T-cell lymphoma, has a very aggressive disease course and is usually fatal.¹⁶ Some of the cases reported for adalimumab occurred in young adult patients with inflammatory bowel disease who were also taking other oral medications, e.g., azathioprine, that can suppress the immune system. There have also been cases of acute and chronic leukemia reported in association with the use of TNF-antagonists including adalimumab. With the current knowledge, a possible risk for the development of lymphomas or other malignancies in patients treated with a TNF-antagonist cannot be excluded.

Patients with UC and CD involving the colon have a substantially increased risk of developing colorectal cancer. The risk for colorectal cancer in CD involving the colon is similar to that of UC of similar duration and extent. Small intestinal cancer occurs at an increased rate in patients with Crohn's enteritis, but the absolute risk remains small.

Extraintestinal malignancies are uncommon in IBD but lymphomas, biliary tract cancers and squamous cell cancers of the skin may occur at an increased rate in IBD patients.^{17,18}

3.1 Safety Information

Adalimumab therapy has a well established and well described safety profile based on extensive postmarketing experience and continued clinical trial patient exposure since the first approved indication in 2002 for rheumatoid arthritis. A detailed discussion of the clinical toxicology, metabolism, pharmacology and safety experience with adalimumab can be found in the current Package Insert. AbbVie is committed to continue to collect safety information including those events that may occur in this trial in order to confirm the established safety profile and to identify unknown potential adverse reactions, rare events and those events with a long latency. AbbVie is participating in an FDA-requested, TNF-inhibitor class wide exploration of the rare appearance of malignancy in patients who are 30 years of age or younger at the time of diagnosis. The risk of malignancy in this age group has not been established and is difficult to study due to its rarity. AbbVie appreciates your attention to the additional reporting requirements needed in this unlikely event, as outlined in Section 7.5 under Adverse Event Reporting.

4.0 Rationale

This protocol describes a non-interventional Registry that will evaluate the long-term safety and effectiveness of Humira as used in routine clinical practice in adult patients (18 years of age or older) with CD, who are candidates for anti-TNF therapy according to the local product label. This Registry study is part of a post-marketing commitment from AbbVie Inc. to the FDA and European Medicines Agency (EMA).

The sample size for the Registry is 5,000 patients. Recent literature data describes a lower expected rate for the adverse event of lymphoma than previous estimates; therefore, following a discussion with the FDA, the registry duration has been extended to 6 years. In addition, follow-up procedures for patients who discontinue the registry have been

added to the protocol to maximize the safety information which may be collected from all registry patients.

The participating physicians, with regard to countries and sites, are representative of the gastroenterologists who will prescribe Humira to patients with CD in North America, Europe, South Africa, New Zealand and Australia. The patients selected for this Registry correspond to the target population in the Humira labels in the participating countries. The patients will receive commercial Humira that will be prescribed per their local prescribing information.

The data collected in this Registry will be complementary to those from the pre-registration studies of adalimumab in CD. The management of the patients in this Registry reflects the current clinical practice. The participating physician is free to determine the appropriate therapy for each patient and make treatment choices as deemed clinically necessary. All patients that consent to take part in the registry will be followed for up to 6 years, providing long-term safety and effectiveness data on Humira in CD.

5.0 Registry Objective

The primary objective of this Registry is to evaluate the long-term safety of Humira in CD adult patients (18 years of age or older) who are treated as recommended in the local product label. The secondary objective is to evaluate long-term effectiveness of Humira in CD patients who are treated as recommended in the local product label.

6.0 Investigational Plan

This is a multicenter, uncontrolled non-interventional Registry of patients with CD treated in a routine clinical setting with Humira. Approximately 5,000 subjects in the US, Europe, Canada, Australia, New Zealand and South Africa will be enrolled.

Physicians will be provided with a study kit that includes a protocol, patient informed consent forms, Serious Adverse Event Report Forms, paper patient questionnaires, and electronic Case Report Forms (eCRFs).

The decision to prescribe Humira (adalimumab) to the patients should be made separately from the decision to enroll them in the Registry.

With patient consent and having met all the inclusion criteria and none of the exclusion criteria, the physician may enroll the patient into the Registry. Physicians are encouraged to treat their patients as they would in their routine clinical practice and in accordance with the local Humira (adalimumab) product label. The physician will then follow the patient during regular office visits at intervals as determined by routine clinical practice or as recommended by national guidelines.

Patient's safety data and information about medications taken for CD will be recorded on eCRFs at study enrollment and during their regularly scheduled visits which are closest to Months 3, 6, 9, 12, 18, 24, 30, 36, 42, 48, 54, 60, 66 and 72. While the physician may deem it appropriate and necessary to have the patient return for intermediate visits during the course of the registry, data will be collected via eCRFs only at the intervals that most closely correspond to those described above.

In an effort to maximize safety data collection, physicians will be asked to do the following:

- Consent and re-enroll patients that were previously discontinued due to the prior P06-134 protocol withdrawal criteria (e.g., patient discontinued Humira). Patients that re-enroll in the Registry will resume data collection via the eCRF process as outlined in the protocol.
- For patients that re-enroll in the Registry, physicians will be asked to collect and report surgeries or hospitalizations and adverse events of special interest (Section 7.1.2) and Crohn's related medication use between registry discontinuation and re-enrollment based on a retrospective review of their patient records.

- For patients that decline re-enrollment for full safety and effectiveness data collection or who have discontinued from the Registry for other reasons, physicians will be asked to obtain the patient's consent to data release for the completion of a simplified Healthcare Provider (HCP) questionnaire on an annual basis. The first data collection period will capture data from the time of patient's discontinuation of the Registry through the start of the direct to HCP process. The questionnaire focuses on the collection of surgeries or hospitalizations and adverse events of special interest and Crohn's related medication use since registry discontinuation. The questionnaire may be completed by the registry physician or the patient's current HCP (if they are no longer under the care of a registry physician). An HCP is not considered a participating investigator in the registry since they are only completing an annual questionnaire on behalf of a former registry patient. Participating registry investigators for which all of their patients have discontinued from registry participation may convert to an HCP status if their patients(s) choose to participate in the HCP process.

If treatment with Humira is permanently discontinued for any reason, patients will be encouraged to remain in the registry or to participate in the direct to HCP process unless consent is withdrawn.

When applicable, information about the effectiveness of Humira therapy will be provided by the patients and their physician. Effectiveness of therapy provided by the patient will be collected with PROs beginning with the registry enrollment visit, at regularly scheduled visits which are closest to Months 3, 6, 9, 12, and every 6 months thereafter, if part of routine clinical assessment. The following PROs will be used: Short Inflammatory Bowel Disease Questionnaire (SIBDQ), Health Care Resource Utilization (Unscheduled Outpatient Visits, Emergency Room Visits and Hospitalizations Questionnaire), and Work Productivity and Activity Impairment (WPAI). There are approximately 20 questions in the PRO assessments and it is expected that it will take approximately 15 minutes to complete them. Effectiveness of therapy will be collected through the Physician's Global Assessment beginning with the Registry enrollment visit and at regularly scheduled visits which are closest to Months 3, 6, 9, 12, and every

6 months thereafter, if part of routine clinical assessment. Effectiveness measures will only be collected for patients receiving Humira.

Serious adverse events (SAE) and adverse events of interest will be recorded throughout the patient's participation in the registry or direct to HCP process and/or until 70 days following discontinuation of Humira/UMIRA administration have elapsed (which ever period is longer).

Adverse events of interest for this Registry include:

- Serious opportunistic infections, e.g., invasive fungal infections and TB
- Lymphoma including hepatosplenic T-cell lymphoma; leukemia, non-melanoma skin cancer (NMSC)
- Other malignancies (excluding lymphoma, leukemia and NMSC which are recorded separately)
- Immune reactions including lupus, lupus-like reactions and serious allergic reactions
- Congestive heart failure (CHF)
- Cerebrovascular accident (CVA)
- Myocardial infarction (MI)
- CNS demyelinating disorders (including Multiple Sclerosis and Guillain-Barré syndrome)
- Hepatic events that are serious or lead to permanent discontinuation of Humira (e.g., persistent liver function test abnormalities, acute liver failure and other serious hepatic events)
- Hematologic events that are serious or lead to permanent discontinuation of Humira (e.g., Aplastic anemia, Granulocytopenia, Granulocytes maturation Arrest, Leucopenia, Neutropenia, Pancytopenia and Thrombocytopenia)
- Worsening or new onset of Psoriasis
- Vasculitis

- Diverticulitis
- Intestinal perforation
- Occurrence of symptomatic intestinal obstruction
- Events leading to premature discontinuation of HUMIRA

Information on all concomitant medications will be captured at the time of enrollment into the Registry. Information on medications taken for CD (including dose changes) and a complete list of all medications taken at the time of a serious adverse events or adverse events of interest will be collected throughout the Registry.

This is a global registry being conducted in the US, Europe, Canada, South Africa, New Zealand and Australia and as such there are multiple local product labels. In Europe, Humira is registered for patients with severe Crohn's disease, while in the other regions it is registered for patients with moderate to severe disease. This protocol has been designed to accommodate all product labels.

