6.2.1 Inclusion Criteria

An adult patient (18 years of age or older) with CD for whom Humira therapy is indicated according to the local product label and who meet the following criteria may be enrolled in this study:

1. Patients to be enrolled must fall into one of the following categories:
 - Patients who are newly prescribed Humira therapy (have never been treated with adalimumab).
 - Patients who are current participants in AbbVie sponsored investigational CD trials, are currently receiving Humira and for whom the treating physician has made the decision to continue with Humira therapy beyond the duration of the investigational trial.
 - Patients who were prior participants in AbbVie sponsored investigational Crohn's disease trials, who have not had dose interruptions since the last dose of registry drug, where the Investigator can provide source documentation of dosing information.
 - Patients who are currently receiving Humira, as per the local product label, who have not had dose interruptions since the induction dose of Humira where the Investigator can provide source documentation of dosing information.
2. Patients willing to consent to data being collected and provided to AbbVie.
3. Patients capable of and willing to give written informed consent and to comply with the requirements of the Registry protocol.

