6.3.2 Effectiveness Variables

Information to evaluate the effectiveness of adalimumab therapy will be collected from patients and their physicians if part of routine clinical assessment. In the event adalimumab therapy is interrupted, effectiveness variables will be collected during the interruption.

The effectiveness of therapy evaluation provided by the subject will be collected with PROs beginning with the study enrollment visit, at regularly scheduled visits which are closest to Months 3, 6, 9, 12, and every 6 months thereafter, if part of routine clinical assessment. The following PROs will be used:

- SIBDQ,
- Health Care Resource Utilization (Unscheduled Outpatient Visits, Emergency Room Visits and Hospitalizations Questionnaire),
- WPAI.

There are approximately 20 questions in the PRO assessments and it is expected that it will take approximately 15 minutes to complete them.

Effectiveness of therapy provided by the study physician will be collected through the Physician's Global Assessment, if part of routine clinical assessment. The following assessments will be collected:

- General Well Being,

- Abdominal Pain,
- Diarrhea,
- Blood in Stool,
- Abdominal Mass,
- Crohn's Disease Related Complications.

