6.4.8 Adalimumab Treatment and Dosing Changes

The participating physician will provide the patient a prescription for HUMIRA, along with instructions for appropriate use. At subsequent protocol-defined study visits the physician will collect the start and stop dates, any dose interruptions and reason for the dose interruption that may have occurred since the last study visit. The dose, dates of administration, any dose interruptions and the reason for the interruption will be captured in the source documents and eCRFs.

Dose interruptions for the study will be defined as patients missing > 1 dose. The reason(s) for interruptions will be captured on the eCRF.

Most clinical data associated with this study will be collected and reported electronically (eCRF) via a web address and secure password. Patient questionnaires will be completed on forms formatted for fax scanning. The site will fax or email completed forms into the designated Study Help Desk.

At the enrollment visit, the physician will complete the Enrollment eCRFs by obtaining and recording all available required information, including visit date, demographic data, concomitant diseases and concomitant medications.

At subsequent visits corresponding to the schedule of assessments ([Table 1](#)), the physician will complete the appropriate eCRF by obtaining and recording all available information. Since this is an observational study conforming to usual clinical practice, data from subject visits that most closely correspond to the schedule of assessment at Months 3, 6, 9, 12, 18, 24, 30, 36, 42, 48, 54, 60 66 and 72 will be accepted. For example, if a patient visits the physician's site at Month 5, this is close to the protocol-defined 6-month study

visit, so data can be collected for this visit. If the same patient unexpectedly returns for a visit to the physician's site at a date closer to the 6-month visit, no further PRO data needs to be collected since the data was previously collected. Safety data that meets the criteria for collection should be collected regardless of protocol-defined study visits.

If a patient completes the 6-year observation period study completion of eCRFs should be completed.

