10.4 Effectiveness Analyses

Effectiveness parameters measured over the course of registry, include change from registry enrollment in the following measures: SIBDQ, Health Care Resource Utilization, WPAI, and Physician's Global Assessment.

The Physician's Global Assessment and SIBDQ scores will be summarized descriptively at each Registry visit. Additionally, changes from Registry enrollment by Registry visit will also be summarized for these outcomes using descriptive statistics. Health Resource Utilization and WPAI will also be summarized with descriptive statistics at each Registry visit.

For efficacy analyses of the "episodic dosing" population, only patients providing evaluations of efficacy at the two timepoints described below will be considered:

- data prior to the interruption in dosing, specifically at/after 12 weeks from enrollment in the Registry study.
- data after the dosing interruption is over, specifically, at/after 12 weeks upon resumption of Humira. For these patients, efficacy data at/after 12 weeks of

the 1st treatment in the Registry and at/after 12 weeks after the restart of Humira treatment during the Registry study will be summarized.

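### The protocol gives two rules for collecting effectiveness during a Humira interruption, collects none after permanent stopping, and pools change from enrollment over new starters and patients already on treatment

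*Protocol*

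**What the plan says.** **Collection.** Section 6.0 states "Effectiveness measures will only be collected for patients receiving Humira". Section 6.3.2 states "In the event adalimumab therapy is interrupted, effectiveness variables will be collected during the interruption". Section 6.4.8 defines the term: "Dose interruptions for the study will be defined as patients missing > 1 dose". Table 1 schedules the Physician's Global Assessment (PGA), SIBDQ, WPAI and resource utilization at every registry visit and sets no condition on Humira status. Collection throughout depends on the assessment being part of the physician's routine practice.

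**Patients who stop.** Section 6.0 adds: "If treatment with Humira is permanently discontinued for any reason, patients will be encouraged to remain in the registry". The alternative offered is the annual healthcare-provider (HCP) questionnaire, for which Section 7.8 excludes effectiveness data.

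**Who enters.** Section 6.2.1 admits patients never treated with adalimumab and three further categories:
- "Patients who are current participants in AbbVie sponsored investigational CD trials, are currently receiving Humira";
- earlier participants in sponsor trials with no dose interruption since;
- "Patients who are currently receiving Humira, as per the local product label", again without interruption since induction.

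**Analysis.** Section 10.4 takes registry enrollment as the reference point for all effectiveness measures. For the PGA and SIBDQ it adds that "changes from Registry enrollment by Registry visit will also be summarized for these outcomes using descriptive statistics". Section 10.2 places all analyses by default on one Safety Population of everyone with at least one dose. The only separate effectiveness analysis in Section 10.4 is for the episodic dosing population.

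**The concern.** The secondary objective is long-term effectiveness, and three features of the text make its main summary hard to read.

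First, about 450 physicians have two rules for a patient whose Humira is interrupted. Some sites will record scores and some will not, so the visit means will mix both practices in unknown proportions.

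Second, a patient who stops permanently may keep attending registry visits, but no effectiveness scores are taken. If patients who stop tend to be those doing badly, the later means look better than the experience of everyone still followed. Data that were never collected cannot be recovered at analysis.

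Third, the enrollment value is a pre-treatment value for new starters and an on-treatment value for everyone else. One pooled mean change answers neither what happens after starting Humira nor whether a response already reached is kept. It also moves with the enrollment mix.

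**Working it through.** **1. Collection rules side by side**

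| Patient's state | Section 6.0 | Section 6.3.2 |
|---|---|---|
| On Humira | collect | collect |
| Interrupted (more than one dose missed) | do not collect | collect |
| Permanently stopped, still in registry | do not collect | silent |
| HCP process | not collected (Section 7.8) | – |

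The second row is a direct conflict. The third row is not a conflict between these two sections. It is a gap in the data that Section 6.0 alone creates.

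**2. Size of the selection after stopping**

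At a given visit, let q be the fraction of patients still in the registry who have permanently stopped Humira, and let m_on and m_off be the mean scores on and off drug.

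- Mean over all still in the registry = (1 − q) × m_on + q × m_off
- On-drug mean minus that mean = q × (m_on − m_off)

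The protocol gives none of q, m_on or m_off. The nearest figure is the attrition model in Section 10.7, which reproduces:

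- Years per patient = (1 − exp(−6 × 0.231)) / 0.231 = 3.246
- Total = 5,000 × 3.246 = 16,230 patient years, as stated
- Share still followed, exp(−0.231 t): 79% at year 1, 63% at year 2, 50% at year 3, 25% at year 6

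The rate of 0.231 comes from time to dropout in two long-term trials. It describes leaving follow-up. It is not a rate of stopping Humira while staying in the registry, so it does not supply q.

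**3. Pooled change from enrollment**

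Let s be the already-treated share, D the mean change in new starters and E the mean change in already-treated entrants.

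- Pooled change = (1 − s) × D + s × E
- If already-treated patients do not change further (E = 0, an assumption): pooled change = (1 − s) × D

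With D = −4 PGA points, assumed for illustration:

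| Already-treated share s | Pooled change |
|---|---|
| 0.2 | 0.8 × (−4) = −3.2 |
| 0.4 | 0.6 × (−4) = −2.4 |
| 0.6 | 0.4 × (−4) = −1.6 |
| 0.8 | 0.2 × (−4) = −0.8 |

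The same effect in new starters reads four times larger at s = 0.2 than at s = 0.8 (−3.2 / −0.8 = 4). The protocol states neither s, D nor E.

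**The case against.** **The two collection sentences can be reconciled by a sensible reader.** Section 6.3.2 could be the specific rule for a pause and Section 6.0 the rule for patients no longer on drug. That is a plausible intent, but the protocol does not say it, and a patient who has missed more than one dose is not receiving Humira in the plain sense of Section 6.0. The conflict stands for interruptions.

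**There is no contradiction on permanent stopping.** This is right. A reader might infer that the two sections also clash there. They do not: Section 6.3.2 does not address it, and Table 1 is a general schedule. The point for these patients is what Section 6.0 leaves out.

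**On-drug effectiveness is a legitimate target.** The objective concerns Humira used as labelled, in an uncontrolled descriptive registry, and scores after stopping reflect whatever therapy follows. This stands in part. An on-drug summary is coherent if it is labelled as such, but it should not be read as the course of all patients followed.

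**The attrition model gives no measure of the selection.** A reader might infer from the 25% at year 6 that, if patients who stop return to no change, the reported figure is D where the true mean is 0.25 × D. The document does not support this. On that model the missing 75% have left follow-up, attend no visits, and would stay missing under any collection rule.

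**Splitting tables is detail for the analysis plan.** The protocol does recognise earlier treatment. Section 10.1 sets Day 1 for earlier commercial users at their first Humira dose and says effectiveness information from then to enrollment will be available. Section 10.3 lists prior therapies and exposure duration as covariates. An analysis plan that is not shown could stratify. This tempers the point, but Section 10.4 as written fixes enrollment as the common reference for everyone, and a covariate list does not change what that pooled summary means.

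**Conclusion.** The concern holds in three limited parts.

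1. Sections 6.0 and 6.3.2 contradict each other on effectiveness data during a Humira interruption and must be reconciled.
2. For patients who stop permanently but remain in the registry, Section 6.0 excludes effectiveness data. Later visit means therefore describe only patients still on Humira. The direction is probably favourable if stopping follows poor response, but the size cannot be derived from the protocol.
3. Sections 10.2 and 10.4 pool pre-treatment and on-treatment reference values. The dilution is in proportion to the already-treated share: pooled change = (1 − s) × D, on the assumption that already-treated entrants do not change further. A reader might take an already-treated share of 30% to 60% as likely, and so a mean change 30% to 60% smaller than in new starters. That range is an assumption with no support in the document.

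The second and third parts can push the reported mean in opposite directions, and no net effect can be given. The primary safety objective and the sample size are unaffected. This is a change worth making for the secondary objective.

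**What to change.** - **State one collection rule** in Sections 6.0 and 6.3.2 that covers both interruption and permanent discontinuation. Preferably, collect the PGA, SIBDQ, WPAI and utilization at registry visits whatever the Humira status. Keep the condition that the assessment belongs to the physician's routine practice, and keep the HCP process excluded.
- **Label two effectiveness summaries** in Section 10.4: *while on Humira* and *all patients still in the registry*.
- **Split every change-from-enrollment table** into newly prescribed and already-treated entrants, and describe the second as maintenance.

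The cost is a few sentences of protocol text, more tables, and a small questionnaire load (the protocol puts the patient questionnaires at about 15 minutes) for off-drug patients at visits they already attend. The split by entry category uses information already collected. The change recovers only patients who stop Humira and stay in the registry. Those who leave, or who move to the HCP process, remain without effectiveness data, so even the second summary stays selected and should say so.
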